5. SUBJECT POPULATION

We will enroll until we have 20 subjects that have expressed a lesion from the induction and complete the treatment period of the study. With the possibility of screen failures and induction failures, we may consent up to 35 patients maximum.

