2.1 Efficacy Endpoints

2.1.1 Primary:

- Proportion of subjects using EED v. those using the Comparator, who do not progress to Stage 3 (vesicle) of a herpes labialis outbreak following UV radiation exposure

2.1.2 Secondary:

- Pain in the lip and surrounding area
- Duration of lesion until healed (loss of hard crust)
- Cumulative lesion area (sum of all lesions)
- Maximum lesion size (size of the largest lesion)

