3. STUDY DESIGN

This will be a randomized, efficacy assessor-blinded, parallel group, pilot study of up to 20 subjects with documented UV induced herpes labialis. We will enroll until we have 20 subjects that have expressed a lesion from the induction and complete the treatment period of the study. With the possibility of screen failures and induction failures, we may consent up to 35 patients maximum.

Potential subjects will be assessed during a screening visit that must take place no greater than 2 weeks prior to the Induction visit. During the screening period, subjects that meet all other entry criteria will undergo UV susceptibility testing to determine their individual MED (minimal erythema dose). UV susceptibility testing takes place over two days with exposure to UV light on specified regions on the subject's back followed by an assessment of the exposed areas 24 hours later to identify the MED.

Subjects who have a measurable MED will be allowed to enroll in the study. Each subject will be randomly assigned in a 1:1 ratio to receive either EED or Comparator.

Subjects that do not have a measurable MED will be considered screen failures or may have repeat MED testing with new values.

At the Induction Visit, subjects will undergo UV radiation at a level 3 times their MED. The exposed area of the lip will be marked with indelible ink and a baseline photograph may be taken.

Each subject will then be randomly assigned in a 1:1 ratio to receive either EED or Comparator. Subjects will be dispensed study medication and instructed how to apply it to the exposed area. Dosing of the study product will be done 5 times daily, beginning at the time that a subject first senses the start of the prodromal phase (Day 1). The EED is a clear viscous eye drop, and the Comparator is a white cream substance. Therefore, the subject and principal investigator will be unblinded, and only efficacy assessments will be done by a qualified trained blinded assessor.

Subjects will be given a diary card to record their pain levels (starting at Day 1), progression of lesion development and any unusual symptoms (not normally seen with their outbreaks).

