Patients will be called daily by the study team after their induction visit to determine the start of prodrome. When the patient first senses the prodromal phase, they need to be seen within 24 hours for the Day 1 visit. Patients that do not have prodromal senses within 7 days of the induction will be considered induction failures. Induction failure patients will be asked to return their study drug to the study team.

On Days 1, 3, 5, and 7 the subject will follow up in person or via virtual MyChart visit with blinded assessor during which the subject's diary card will be reviewed and compliance with dosing checked. If the subject has noted any unusual symptoms, these will be discussed with medical personnel to determine if a treatment emergent adverse event has occurred or, if the subject has not started treatment, whether their medical history should be updated. If possible, the lesion will be measured. A photo will be taken of the irradiated area (as marked at the induction visit). More study drug may be dispensed as needed. Most subjects' lesions will have resolved by day 7, and they will end study treatment after 7 full days of

treatment. If lesion has not resolved by day 7, the maximum number of days the patient may use study drug treatment is 10 days. An end of study (EOS) visit will occur as soon as their lesion is healed or Day 10, whichever comes first.

The EOS visit (Day 10) is expected to be the final study visit. EOS will occur when a subject's lesion is fully healed or Day 10 (whichever comes first). A photo will be taken of the irradiated area, the diary card will be carefully reviewed and study product (including empty containers) will be collected. Subjects who developed a lesion that has not yet healed will be given the option to begin taking a prn medication that has been previously prescribed to treat an outbreak.

If an adverse event has occurred but has not resolved by the EOS visit, the subject will be contacted once weekly, and status of the AE noted until such time as the event has resolved.

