6.1.2 Induction Visit

Upon reporting to the clinic for their induction visit, the subject will be randomized to receive either EED or Abreva. The following assessments will then be performed to establish baseline values prior to dosing:

- Review of Medical History and Concomitant Medications for any changes between Screening and Day 1 (Treatment emergent AEs are collected in this study beginning with first instance of dosing. Any unusual symptoms prior to the start of dosing will be recorded, if appropriate, as an update to the subject's medical history).

- Limited Physical Exam to check for any changes between Screening and Day 1(changes in PE after start of dosing will be assessed as possible treatment emergent AEs)

If the subject remains qualified for the study:

- They will be dispensed study product (EED or Abreva) and instructed to use it 5 times daily beginning when they first sense a prodrome or see a lesion (they will be asked to note the day and time of their first dose on their diary card).
- They will be given a diary card and instructed how to complete it. A practice diary completion may be done to ensure that subjects know how to complete the diary.

Subjects will then be discharged from the clinic with an appointment to return on Day 3 via virtual video call. They will be instructed to bring their Diary Card and the tube/bottle of study product that they have received.

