6.1.3 Day 1 Visit

Day 1 visit will occur within 24 hours of experiencing signs or symptoms of a cold sore. The patient will start applying study drug as soon as they notice signs or symptoms of a cold sore. The subject will present for a follow up appointment in clinic or via virtual video call consisting of:

- Review of the subject's diary card to identify possible treatment emergent adverse events.
- Assessment of the subject's pain on a visual analog scale.
- Measurement of the lesion will be taken (if lesion is present).
- Photographs of area exposed to UV radiation may be asked to be taken by subjects and uploaded into their MyChart account. If patients are present in clinic, photographs will be taken by study staff.
- If the subject has experienced a prodrome or lesion they should have started dosing. The study staff will review their dosing compliance and examine the study product tube/bottle. If the subject is not complying with the dosing regimen, the study staff will determine whether non-compliance is serious enough to warrant terminating the subject's participation. Otherwise, minor non-compliance should be noted, and the subject should be retrained on how to dose themselves.

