6.1.4 Study Days 3, 5, and 7 Visits

On Days 3, 5, and 7, the subject will present for a follow up appointment in clinic or via virtual video call consisting of:

- Review of the subject’s diary card to identify possible treatment emergent adverse events.
- Assessment of the subject’s pain on a visual analog scale.
- Measurement of the lesion will be taken (if lesion is present).
- Photographs of area exposed to UV radiation may be asked to be taken by subjects and uploaded into their MyChart account. If patients are present in clinic, photographs will be taken by study staff.
- If the subject has experienced a prodrome or lesion they should have started dosing. The study staff will review their dosing compliance and examine the study product tube/bottle. If the subject is not complying with the dosing regimen, the study staff will determine whether non-compliance is serious enough to warrant terminating the subject’s participation. Otherwise, minor non-compliance should be noted, and the subject should be retrained on how to dose themselves.

Once patients reach the Stage 2/3 lesion their lesion may be swabbed for viral culture (HSV PCR). If the patient reaches Stage 2/3 over the weekend, the lesion will not be swabbed. We will reserve this for the first five patients but may continue to do all patients to ensure lesion is in fact a cold sore and not a reaction to the UV radiation.

6.1.5 EOS – End of Study Visit (Day 10 – or after subject’s lesion has fully healed)

An EOS visit will occur after the subject’s lesion has fully healed or Day 10 (whichever comes first), the subject will present to the clinic for a follow up appointment in clinic or via virtual video call consisting of:

- Review of the subject’s diary card to identify possible treatment emergent adverse events. If the subject has an AE that has not resolved by this time, the site staff will explain to the subject that they will be called every week to check on the status of the AE, until it is resolved.
- Assessment of the subject’s pain on a visual analog scale.

- Photographs of area exposed to UV radiation may be asked to be taken by subjects and uploaded into their MyChart account. If patients are present in clinic, photographs will be taken by study staff.

The subject's diary card and all tubes//bottles of study product (empty, partially used or unused) will be collected and the subject will be released from the study.

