7. EFFICACY EVALUATIONS

7.1 Number of subjects that experience prodrome (Stage 1) but do not progress to vesicles (Stage 3) by completion of treatment

The Principal Investigator or his designee will review all photographs taken from Day 1 through the EOS visit against the onset of prodrome date and the date of healing or 7 full days of treatment noted on the subject's diary card. They will then determine the duration of the HSV outbreak (prodrome to healed). This may or may not agree with the subject's assessment of "healed" but should be based on the collective information gathered during the subject's time on study. The blinded assessor will assess the prodrome and/or lesion at every clinic visit starting at day 3. The blinded assessor will only be responsible for the rating of the prodrome and or/lesions. The blinded assessor will not be performing safety evaluations. The unblinded staff will instruct the subject to not talk with the blinded assessor about which treatment they have been using.

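### Does counting only subjects who express a lesion toward the 20 leave the trial's size undefined, when the primary success is an outbreak that never forms vesicles?

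*Combined protocol and SAP*

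**What the plan says.** The enrolment sentence stands in the synopsis (Subjects), Section 3 and Section 5: "We will enroll until we have 20 subjects that have expressed a lesion from the induction and complete the treatment period of the study". Sections 3 and 5 then give the cap and its reason: "With the possibility of screen failures and induction failures, we may consent up to 35 patients maximum".

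The primary endpoint in Section 2.1 is the proportion of subjects "who do not progress to Stage 3 (vesicle) of a herpes labialis outbreak following UV radiation exposure". Section 7.1 measures it as "Number of subjects that experience prodrome (Stage 1) but do not progress to vesicles (Stage 3) by completion of treatment".

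Induction failure is defined by prodrome, not by lesion. Section 3 says: "Patients that do not have prodromal senses within 7 days of the induction will be considered induction failures".

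Elsewhere a prodrome and a lesion are separate events. Section 6.1.2 has dosing start "beginning when they first sense a prodrome or see a lesion", and Section 6.1.3 measures a lesion only when there is one. The synopsis (Efficacy Assessments) links lesion appearance to Stage 3, whereas Section 6.1.4 also uses the word for Stage 2.

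The Per Protocol set in Section 9.1 takes completers who were not induction failures and does not require a lesion.

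**The concern.** The plan has no sample-size calculation, so the enrolment sentence alone fixes how many people are treated. If a lesion means Stage 3, no primary success counts toward the 20. If Stage 2 is enough, successes that stop at Stage 1 still do not count. On either reading, aborted outbreaks come on top of the 20, and the more often treatment works in either arm, the more people are treated.

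That sits badly with the design statement, which caps the study at 20, and with Section 8.2, whose closing sentence has the last safety review cover 20 in all. The cap of 35 is explained by screen and induction failures only, so it appears to leave no room for aborted outbreaks. The team might go on treating past 20, or report a missed target while holding 20 or more usable completers.

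**Working it through.** **The plan's own figures.** Neither 20 nor 35 is derived in the documents, so neither can be reproduced or called wrong. Reaching 20 from 35 needs 20/35 = 57.1% of consented patients to count, so at most 15 may be lost for all reasons together.

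**Assumed inputs.** The documents give neither of these, so ranges are shown.
- L: share of consented patients lost to screen failure, induction failure or non-completion; 20%, 30%, 40%.
- u: share of prodromal completers not counted toward the 20. On the Stage 3 reading u is the non-progression rate (20% to 50%). On the Stage 2 reading it is the share stopping at Stage 1 (5% to 20%). If the sentence means that the induction worked, u = 0.

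**Chance of reaching 20 counted within 35 consents.** Counted subjects X ~ Binomial(35, (1−L)(1−u)). For example, L = 20% and u = 30% give 0.8 × 0.7 = 0.56, and P(X ≥ 20) = 0.52.

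| u | L = 20% | L = 30% | L = 40% |
|---|---|---|---|
| 0 | 0.9995 | 0.96 | 0.70 |
| 5% | 0.996 | 0.91 | 0.56 |
| 10% | 0.98 | 0.81 | 0.42 |
| 20% | 0.85 | 0.52 | 0.18 |
| 30% | 0.52 | 0.21 | 0.05 |
| 40% | 0.18 | 0.05 | 0.01 |
| 50% | 0.03 | 0.01 | 0.001 |

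**What a missed count means for the primary test.** Counted subjects are a subset of treated completers. Enrolment therefore stops early only when there are already at least 20 completers, and otherwise runs to 35 consents. Fewer than 20 completers can arise only if all 35 consents yield fewer than 20, so P = P(Binomial(35, 1−L) ≤ 19) = 0.0005, 0.036, 0.30 at L = 20%, 30%, 40%, whatever u is. At L = 20% and u = 30%, the chance of missing the count while still holding 20 or more completers is 0.9995 − 0.516 = 0.48. That would be a missed label, not a shortfall in data.

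**Bias.** The stopping count pools both arms and takes no account of allocation, and all completers are analysed whether or not they counted. I simulated the literal Stage 3 rule (simple 1:1 allocation, L = 20%, at most 35 consents) with assumed non-progression of 0.5 v 0.2. The mean estimated difference was 0.298, against a true 0.30.

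**What rewording would buy or cost.** Simulation at L = 20%, stopping at the 20th counted completer or 35 consents. The alternative counts every prodromal completer and stops at 20, giving 20(1−u) Stage 3 lesions on average.

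| Non-progression u | Treated completers, literal rule | Treated completers, alternative | Stage 3 lesions, literal rule | Stage 3 lesions, alternative |
|---|---|---|---|---|
| 20% | 24.6 | 20.0 | 19.7 | 16 |
| 30% | 26.6 | 20.0 | 18.6 | 14 |
| 40% | 27.7 | 20.0 | 16.6 | 12 |
| 50% | 28.0 | 20.0 | 14.0 | 10 |

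**Passages that support the induction-worked reading.** Section 3 makes induction failure turn on prodrome. Sections 3 and 5 explain the cap by screen and induction failures, which is complete if everyone whose induction works counts. Section 9.1 analyses everyone who was not an induction failure. Section 9.2 groups recurrences that never ulcerate with ulcerative ones under a label that calls them all lesions.

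**The other totals.** The 20 in the design statement (synopsis and Section 3) is qualified as subjects with a documented induced outbreak, which can be the same counted unit. Section 8.2's working rule already covers everyone who has reached EOS. Its figure of 20 appears only in a closing restatement that is loose anyway, since it has groups of five raise the total by 10.

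**The case for a change.** The strongest case for a change is that the protocol repeatedly separates prodrome from lesion (synopsis, Sections 6.1.2 and 6.1.3) and once ties lesion appearance to Stage 3, so the literal reading is not far-fetched. With no sample-size calculation, this sentence is all that tells staff when to stop inducing and treating people. Two of three readings make that number depend on the outcome. The correction is one sentence in three places, and if the sponsor meant that the induction worked, it would simply say so.

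The ambiguity stands: the lesion has no stage, and the documents do not settle it. The consequence claimed for it does not. Open-ended treatment is ruled out by the cap of 35. No success is dropped from the analysis, and no reading leaves the primary test with fewer completers. The cap is also not specifically a lesion problem: at u = 0 and L = 40% the chance of reaching 20 is still only 0.70.

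Nor is the proposed wording neutral. Three of the four secondary endpoints concern the lesion itself, and Section 6.1.4 worries about a UV reaction being mistaken for a cold sore. A sponsor could reasonably want expressed lesions, and counting self-reported prodromes would override that choice.

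**Conclusion.** No change to the plan follows. The sentence is loose, but either way of resolving it leaves the primary analysis sound. If it means a successful induction, the target, the cap and the other totals agree, and the gap is one of wording that the study team can fill sensibly. If it means a lesion at a named stage, the plan trades a fixed number treated for more data: at an assumed 20% loss, about 25 to 28 treated completers instead of 20, and about 4 more Stage 3 lesions (19.7 v 16 at 20% non-progression, 14.0 v 10 at 50%), bounded by 35 consents. For a pilot with no power claim that is a fair trade.

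The sizes rest on assumed L and u. They also ignore overshoot from subjects already induced when the target is met, and they treat completing treatment as equivalent to attending every visit, although Section 9.1 asks for the latter. The finding that fewer than 20 treated completers is equally likely on every reading does not depend on u.

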5.1 Inclusion Criteria

To be eligible for enrollment, a subject must meet the following criteria:

1. Understands the requirements of the study and provides written informed consent prior to undergoing any study-related procedures.

2. Subject is a male or female between the ages of 18-80 years old, inclusive.
3. Fitzpatrick skin type II or III.
4. History of at least one year of herpes labialis induced by UV exposure.
5. Able to recall exact location of most common or most recent outbreak.
6. History of at least 50% of cold sore outbreaks occurring with UV (sun) exposure.
7. At least 1 HSV-1 outbreak within the past 12 months.
8. Experiences prodromal symptoms before HSV-1 outbreaks.
9. Subject is willing and able to comply with protocol-specified dosing, visits to the clinic and tracking of pain.

5.2 Exclusion Criteria

Subjects will be excluded from the study if they meet any of the following criteria:

1. Outbreak <2 weeks prior to enrollment.
2. History of herpes simplex vaccine.
3. On antiviral suppression within the past 30 days.
4. Requires more than acetaminophen for pain from recurrent HSV outbreaks.
5. On any systemic or topical steroid, immune suppressant or chemotherapeutic agent within the past 14 days.
6. Use of tanning beds, history of sunburn, or beach vacation <2 weeks prior to enrollment.
7. History of photosensitivity, lupus erythematosus, or current use of photosensitizing medication.
8. Current immunosuppressed state due to underlying disease (i.e. HIV infection) concomitant treatment (i.e. chemotherapy).
9. Current upper respiratory tract infection or any active illness that could trigger cold sores or affect overall health of the patient or the assessment of the study agent.
10. Pregnant or intending to become pregnant during the study.
11. Abnormal skin conditions in the area of the recurrent HSV1 outbreaks.
12. Enrolled in another clinical trial within the past 30 days.
13. Previously treated with EED.
14. On any analgesics or NSAIDs that cannot be stopped during the study.
15. Alcohol or drug abuse.

6. STUDY PROCEDURES

6.1 Study Visits

6.1.1 Screening Visit (Days -14 to 0)

No more than 14 days prior to their planned start of study, subjects will report to the dermatology clinic for the following screening procedures:

- Presentation, review and signing of the informed consent.
- Review of their medical history.
- Review of HSV history.
- Assist with setting up MyChart account.
- Review of Inclusion and Exclusion criteria.
- Limited Physical Exam – to ensure that there are no co-morbidities that may interfere with study compliance or results.
- Notation of any concomitant medications the subject is currently taking (and that do not conflict with entry criteria).

ONLY IF the subject meets all entry criteria and is considered by the Investigator to be able to comply with and complete all study procedures, may they proceed to the final screening procedure of UV Susceptibility and Calculation of MED (refer to Study Manual for detailed instructions) consisting of:

- Exposure to UV Radiation.
- Assessment of Exposed Area – no more than 24 hours after exposure.

6.1.2 Induction Visit

Upon reporting to the clinic for their induction visit, the subject will be randomized to receive either EED or Abreva. The following assessments will then be performed to establish baseline values prior to dosing:

- Review of Medical History and Concomitant Medications for any changes between Screening and Day 1 (Treatment emergent AEs are collected in this study beginning with first instance of dosing. Any unusual symptoms prior to the start of dosing will be recorded, if appropriate, as an update to the subject's medical history).

- Limited Physical Exam to check for any changes between Screening and Day 1(changes in PE after start of dosing will be assessed as possible treatment emergent AEs)

If the subject remains qualified for the study:

- They will be dispensed study product (EED or Abreva) and instructed to use it 5 times daily beginning when they first sense a prodrome or see a lesion (they will be asked to note the day and time of their first dose on their diary card).
- They will be given a diary card and instructed how to complete it. A practice diary completion may be done to ensure that subjects know how to complete the diary.

Subjects will then be discharged from the clinic with an appointment to return on Day 3 via virtual video call. They will be instructed to bring their Diary Card and the tube/bottle of study product that they have received.

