Design	
This will be a randomized, efficacy assessor-blinded, parallel group, pilot study of up to 20 subjects with documented MED induced herpes labialis.
 
Potential subjects will be assessed during a screening visit that must take place no greater than 2 weeks prior to the lesion induction visit. During the screening period, subjects that meet all other entry criteria will undergo UV susceptibility testing to determine their individual MED (minimal erythema dose). UV susceptibility testing takes place over two days with exposure to UV light on specified regions on the subject's back followed by an assessment of the exposed areas 24 hours later to identify the MED. Subjects who have a measurable MED will be allowed to continue to the induction visit. Patients that do not have a measurable MED response will be considered screen failures or they may have repeat MED testing with different levels.
 
At the Induction Visit, subjects will undergo UV radiation at a level 3 times their MED. The exposed area of the lip will be marked with indelible ink and a photograph may be taken. Each subject will then be randomly assigned in a 1:1 ratio to receive either EED or Comparator. Subjects will be dispensed

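### Section 6.1.2 randomises on arrival at the Induction Visit, before continued eligibility is confirmed, while the synopsis and Section 3 randomise after irradiation

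*Combined protocol and SAP*

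**What the plan says.** Section 6.1.2 gives an explicit order for the Induction Visit. It opens with "Upon reporting to the clinic for their induction visit, the subject will be randomized to receive either EED or Abreva". Next come reviews of medical history and concomitant medications and a limited physical exam, each looking for changes since screening. Product and diary card are then given out under the condition "If the subject remains qualified for the study". The section does not mention the lip irradiation.

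The Design row of the synopsis gives a different order. Irradiation at 3 times the MED comes first, then marking of the lip and an optional photograph, and then: "Each subject will then be randomly assigned in a 1:1 ratio to receive either EED or Comparator". Section 3 repeats that sequence. Section 3 also carries a second randomisation sentence, placed just after the MED requirement and with no timing attached: "Each subject will be randomly assigned in a 1:1 ratio to receive either EED or Comparator".

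On the MED, the synopsis says "Subjects who have a measurable MED will be allowed to continue to the induction visit", and Section 3 says "Subjects who have a measurable MED will be allowed to enroll in the study". Section 6.1.1 makes the MED test the final screening procedure and lists the reading of the exposed skin there. The Section 10 schedule marks only the exposure at Screening and puts the MED reading in the Induction Visit column.

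On knowledge of the arm, Section 3 states that "the subject and principal investigator will be unblinded", because the two products look different. Section 4.3 has the Investigator generate a simple 1:1 code.

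**The concern.** Eligibility should be settled before allocation, so that nobody who knows the arm decides who stays in. Section 6.1.2 reverses this. With an unblinded principal investigator and an Investigator-generated code, the decision that a subject no longer qualifies could be made by someone who knows the assignment. Some entry criteria call for judgement: exclusion criterion 9 in Section 5.2, for example, turns on whether an illness might trigger cold sores or affect the assessment of the product.

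At stake is the comparability of the arms for the primary endpoint, the proportion not progressing to Stage 3. Section 9.2 compares it between arms with a chi-square test. Any selective removal would also be invisible, because no all-randomised population is defined.

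**Working it through.** No arithmetic applies. The plan states no figure on this point, and it gives no rate of removal at the Induction Visit from which one could be derived. The check is a comparison of the sections.

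1. **Order of steps.**

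| Source | Order stated |
|---|---|
| Section 6.1.2 | randomise on arrival, then history, medication and exam review, then eligibility condition, then dispense |
| Synopsis, Design | measurable MED, then irradiation, then randomise, then dispense |
| Section 3, sentence after irradiation | irradiation, then randomise, then dispense |
| Section 3, sentence after the MED requirement | no time marker |

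Two clear positions conflict: on arrival, and after irradiation. Nothing says which governs.

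2. **Does 6.1.2 by itself put allocation before the eligibility decision?** Yes. The section says that the reviews are performed after randomisation, and the eligibility condition comes after the reviews. This does not depend on the schedule table.

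3. **Could the decision-maker know the arm?** Section 3 leaves the principal investigator unblinded, and Section 4.3 has the Investigator produce the code. Neither section describes a step that withholds the assignment until eligibility is settled. The documents do not say that the arm is disclosed at the moment of randomisation, so knowledge of the arm is possible rather than stated.

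4. **Would a removal at that point appear in any analysis?** Product is dispensed only after the check, so a removed subject has used none. The Safety population in Section 9.1 needs at least one day of use, so the subject is outside it. The Per Protocol population needs attendance at all study visits, so the subject is outside that too. Section 9.1 defines no other population.

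5. **MED reading.** The synopsis, Section 3 and Section 6.1.1 all treat the MED as a screening matter. Section 10 alone shows the reading at the Induction Visit. This is a separate, smaller inconsistency.

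**The case against.** The strongest reply is that 6.1.2 is loosely drafted and not a real instruction to allocate early. It omits the irradiation, so it is not a full account of the visit. The entry criteria are applied in full at screening under 6.1.1, and the reviews in 6.1.2 are described as baseline checks over at most 14 days. Product appearance, the stated reason for unblinding, comes into play only at dispensing, which follows the check. These points lower the likelihood of harm. They do not remove the stated order, or the eligibility decision that 6.1.2 places after it. The pilot label does not answer the point either, since the primary endpoint is a comparison between randomised arms.

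A second reply is that the bias risk lies mainly in who holds the code. That stands in part: an investigator holding a simple list could know the next arm wherever randomisation is placed. Reordering is necessary but does not conceal the code.

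A reader might go further in three ways that the documents do not support:

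- **Allocation before the MED is known.** This arises only by joining one Section 10 column to the on-arrival wording, against the synopsis, Section 3 and Section 6.1.1. Irradiation at 3 times the MED also needs a MED, so the order in the synopsis is safe here. Section 10 lists the reading above randomisation; row order is not a stated sequence, but nothing in the table puts allocation first.
- **A third randomisation time, from the first of Section 3's two sentences.** That sentence carries no timing.
- **A number exposed, from the gap between 35 consented and 20 completers.** Section 3 attributes that allowance to screen failures and induction failures. The synopsis and Section 3 place screen failure before allocation, and induction failures follow allocation under any order. The gap does not measure this defect.

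**Conclusion.** The concern holds in a limited form. Section 6.1.2 as written allocates before continued eligibility is confirmed and conflicts with the synopsis and with the timed statement in Section 3. Under that order a requalification decision could be made with the arm known, and a subject then removed would be in neither defined population.

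The size of any bias cannot be quantified from the documents and may be zero. It depends on whether anyone is removed at the check, whether the arm is known at that moment, and whether the removal is related to prognosis. The conclusion assumes that staff follow 6.1.2 literally, which is reasonable for the section that describes the visit. The placement of the MED reading in Section 10 is a consistency matter only. The correction should be made because it reduces a real risk at almost no cost.

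**What to change.** 1. In Section 6.1.2, put the history, medication and exam reviews first, document continued eligibility, add the irradiation, and only then randomise and dispense, matching the synopsis.
2. In Section 3, delete the untimed randomisation sentence that follows the MED requirement and keep the one after irradiation.
3. Report by arm and reason every subject allocated but removed before dosing. Giving the reason separates induction failures, which follow allocation under any order, from eligibility removals.
4. As a secondary edit, move the MED reading in Section 10 to screening, or state that it precedes irradiation and randomisation.

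The cost is a reordering within one section, one deleted sentence, one schedule entry and a short listing. The eligibility review and the MED test are already planned, so subjects undergo nothing new. Concealment of the Investigator's code needs its own provision; these edits do not supply it.
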